13.2 Sensitivity Analysis

In order to check the robustness and validity of the primary analysis the analysis described under Section 13.1 Primary Analysis will be repeated using the PP. For this analysis filters used after a patient crossed over treatment to the other study treatment group will not be included.

In order to assess a potential impact of informative censoring on the primary efficacy analysis, a sensitivity analysis will be carried out on the FA. The analysis of the primary efficacy endpoint will be repeated for 4 scenarios using the following assumptions for cases where therapy (ie, a filter) was discontinued for reasons other than filter clotting:

- 1. Assume for each of these cases in the Prismocitrate 18 group that filter clotting (the primary event of interest; please see Section 5.5.1 Primary Efficacy Endpoint) occurred at the time of therapy discontinuation for reasons other than filter clotting; Assume for each of these cases in the Control group that filter clotting occurred at the time of therapy discontinuation for reasons other than filter clotting.
- 2. Assume for each of these cases in the Prismocitrate 18 group that filter clotting occurred at the time of therapy discontinuation for reasons other than filter clotting; Assume for each of these cases in the Control group that filter clotting occurred at the largest event time observed in the Control group.
- 3. Assume for each of these cases in the Prismocitrate 18 group that filter clotting occurred at the largest event time observed in the Prismocitrate 18 group; Assume for each of these cases in the Control group that filter clotting occurred at the time of therapy discontinuation for reasons other than filter clotting.
- 4. Assume for each of these cases in the Prismocitrate 18 group that filter clotting occurred at the largest event time observed in the Prismocitrate 18 group; Assume for each of these cases in the Control group that filter clotting occurred at the largest event time observed in the Control group.

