13. EFFICACY PARAMETERS

13.1 Primary Analysis

The primary endpoint of the study, extracorporeal circuit life, will be analyzed as a time-to-event endpoint (survival analysis).

The extracorporeal circuit life of a filter that is replaced due to continuous use for 72 hours, will be censored for the statistical analysis. Likewise, filters that are in use when the end of the observation period of 120 hours is reached, will be censored at their current duration of usage at the end of the observation period. Filters that are replaced any time CRRT is stopped for reasons other than filter clotting (including drop-outs and switches to therapies other than Prismocitrate 18 or control), will be censored at their current duration of usage. Only filters that are replaced due to filter clotting or excessive transmembrane pressure as indicated by system alarms/conditions and confirmed by an Independent Adjudicator will be considered 'events' in the statistical survival analysis.

The context and data/time of two alarms (as below) used in the independent adjudication

- Warning: Filter Clotted" and/or
- "Advisory TMP Too High"

will be derived from the data card. The date and time of first occurrence of one or both alarms above that could not be successfully mitigated by the study site, will be considered as the end of the filter life if the event (alarm) is confirmed to be caused by filter clotting by the independent adjudicator. Also, the date and time recorded on data card for filter start, replace and/or end will be used to calculate the filter life during the independent adjudication.

If the reason for a filter change recorded on the eCRF is different from the indication from adjudication result (e.g. eCRF recorded a reason for filter change for any reasons other than the two alarm, but the adjudication result showed as filter clotted), the adjudication result will be used to determine if it is considered an 'event' in the statistical survival analysis.

In some scenarios, where no independent adjudication could be performed (e.g. missing data card file), the eCRF recorded filter start, end, and change reason will be used in the analysis of filter life.

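### SAP 13.2's informative-censoring scenarios can date a clot before a circuit had stopped running, and do not say whether 72 h changes and circuits running at 120 h are re-coded as clots

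*SAP*

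**What the plan says.** SAP 13.1 names three kinds of circuit that are censored in the primary analysis:

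- Planned changes: "The extracorporeal circuit life of a filter that is replaced due to continuous use for 72 hours, will be censored for the statistical analysis".
- The end of observation: "filters that are in use when the end of the observation period of 120 hours is reached, will be censored" at their current duration.
- Other stops: "Filters that are replaced any time CRRT is stopped for reasons other than filter clotting", with drop-outs and therapy switches given as examples.

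SAP 13.2 then repeats the analysis under four scenarios "for cases where therapy (ie, a filter) was discontinued for reasons other than filter clotting". Each such circuit becomes a clot, timed as follows:

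| Scenario | Prismocitrate 18 | Control |
|---|---|---|
| 1 | own stop time | own stop time |
| 2 | own stop time | largest Control event time |
| 3 | largest Prismocitrate event time | own stop time |
| 4 | largest Prismocitrate event time | largest Control event time |

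The late rule for Control reads "filter clotting occurred at the largest event time observed in the Control group"; for Prismocitrate it reads "filter clotting occurred at the largest event time observed in the Prismocitrate 18 group". Protocol 8.5.1 uses equally open wording for the affected cases and leaves the detail to the SAP. The SAP's document history (version 3.0) records that this analysis was added at FDA request.

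**The concern.** A circuit that ended without clotting after t hours is known not to have clotted before t. Scenarios 2 to 4 can still give it a clot time below t, because nothing ties the imputed time to the circuit's own run time.

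Separately, the scope turns on one phrase. A set changed at 72 h, or ended because observation closed at 120 h, did literally end for a reason other than clotting. Those ends are administrative. Re-coding them as clots tells the reader nothing about informative censoring, and it turns the circuits that lasted longest into failures. This is the only planned check aimed at informative censoring, and two programmers could code it differently and reach different conclusions.

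**Working it through.** **1. The plan's own figures.** SAP 13.2 states none. The power of over 90% in SAP 5.2 cannot be reproduced, because the medians, filters per patient and drop-out rate are blacked out. The boundary can: exp(-9.488/2) = 0.0087, and c(1 + ln(1/c)) = 0.008705 x (1 + 4.744) = 0.0500.

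**2. Impossible times, from the text alone.** Let t be the run time of a circuit that did not clot and M the largest event time in its arm. The rule sets the clot at M, which contradicts the data whenever M < t. Sets are capped at 72 h, so on the literal reading every 72 h circuit is moved back if M is below 72 h. In simulated trials with 30 h medians in both arms, the largest Control event averaged 69.1 h and was 56.0 h at the lowest. A 72 h circuit would then be recorded as clotted 72 - 69.1 = 2.9 h, or 72 - 56.0 = 16.0 h, too early.

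**3. Scope, side by side.** SAP 13.1 uses the phrase only for its third class. SAP 5.2 ties similar words to drop-out, and SAP 6.2.2 lists 72 h use apart from other stops. These favour a narrow reading. SAP 5.5.1, however, puts every replacement other than at end of circuit life in one censored group, and 13.2 makes the filter the unit. Neither reading is stated.

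**4. Simulation inputs.** From the plan: 80 patients per arm, 72 h cap per set, 120 h cap per patient, all circuits included, clustered log-rank test, two-sided 5%. Assumed: exponential circuit life, gamma patient frailty (variance 0.3 to 0.5), the medians shown, and equal non-clot stop rates in both arms. There were 150 to 400 trials per setting.

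**5. How many circuits change class.** At 30/60 h (Control/Prismocitrate) with moderate interruptions, the literal reading adds 31 + 49 = 80 administrative ends to 88 real Prismocitrate clots (80/88 = 91% more). It adds 21 + 49 = 70 to 175 in Control (70/175 = 40% more).

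**6. Trials significant in favour of Prismocitrate.**

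| Medians (h) | Scenario | Literal | Narrow or fixed |
|---|---|---|---|
| 20/40, stops 1/150 per h | 2 | 0% (51% wrong way) | 55% |
| 20/40, stops 1/150 per h | 4 | 55% | 99% |
| 15/60 | 2 | 33% | 97% |
| 15/60 | 4 | 76% | 100% |
| 30/300 | 2 | 25% | 97% |
| 30/300 | 4 | 25-32% (25-27% wrong way) | 100% |
| 15/100 | 2 | 92% | 100% |
| 30/60, more interruptions | 2 | 0% | about 2% |

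At 30/300 h the primary result is significant in 100% of trials. Read through the Fisher combination, Scenario 2 there goes from 19% (literal) to 95% (fixed), the same pattern.

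**7. Which part does the damage.** In Scenario 2 it is mainly the 120 h ends. At 30/300 h, adding only those to the narrow class gives 10%, and adding only the 72 h changes gives 100%. In Scenario 4 it is mainly the back-dating. At 30/300 h, adding only the 72 h changes gives 42%, while the literal class without back-dating gives 97%. Scenario 1 involves no back-dating and hardly changes.

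**8. Back-dating on the narrow reading.** It affects about 0.3 to 5 circuits per trial and moves significance by 2 points or less. At 15/60 h, Scenario 2 gives 97% with and without a floor.

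**9. No true effect (30/30 h).** Literal Scenario 3 favours Prismocitrate in 100% of trials. Literal Scenario 4 is significant for Prismocitrate in 45% and against it in 55%. After the fix these are 95%, and 20% and 23%.

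**10. Frequent other-cause stops.** Narrow Scenario 2 is significant in 55%, 3% and 0% of trials at 20/40 h with stop rates of 1/150, 1/100 and 1/75 per h. At 24/60 h it is 89%, 16% and 0%.

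**The case against.** The strongest reply is that the damaging reading is not the one the SAP intends. SAP 13.1, 5.2 and 6.2.2 all point to the narrow class, the stated purpose is informative censoring, and a filter still in use at 120 h is hardly discontinued. On that reading the impossible times are few and have almost no effect on significance. Scenario 2 is also a deliberately one-sided worst case, and the analysis carries no decision rule.

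Most of this stands, and it limits the size of the point. It does not remove it. The narrow class has to be inferred, SAP 5.5.1 supports the wider grouping, and a rule that can date a clot to a time when the circuit was known to be running is wrong however seldom it applies.

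A reader might infer that the stress test as written will erase a true effect. The documents do not support that. It needs the less favoured reading together with medians and stop rates that are blacked out. Step 10 shows that Scenario 2 can remove the effect under the narrow reading too, so not all of the loss comes from the wording. Nor does the fault run only against Prismocitrate: step 9 shows that, with no true effect, it can favour either arm.

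**Conclusion.** Both faults hold, as defects in a supportive analysis. The missing floor on the imputed time is wrong on any reading but numerically small if only other-reason stops are re-coded. The open scope is an ambiguity. Read literally, administrative ends become clots in all four scenarios, and the check is distorted mainly in Scenarios 2 and 4. The loss runs from slight (15/100 h) to total (20/40 h), under assumed medians and stop rates and equal stop rates in both arms. The primary test and the 0.0087 boundary are untouched. This should be corrected, but the trial's main conclusion does not depend on it.

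**What to change.** Add two sentences to SAP 13.2:

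1. The four scenarios apply only to circuits stopped for reasons other than clotting, the 72 h change or the 120 h end; the last two stay censored as in SAP 13.1.
2. Where a scenario uses the arm's largest event time, the imputed clot time is the later of that time and the circuit's own run time.

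No new data are needed and the primary analysis does not change. Settling the text before unblinded results are seen also removes a later choice between codings. One weakness remains: Scenarios 2 to 4 still rest on the single largest event in an arm. That is why step 9 shows Scenario 4 significant in 20% and 23% of null trials after the fix, so its result should be read with that in mind.

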13.3 Secondary Analysis

A descriptive summary of systemic and post-filter blood iCa²⁺ concentrations as assessed at baseline (systemic only), 1 hour and every 6 hours during the 120 hours evaluation period and at 120 hours or end of the Evaluation period will be provided by treatment group. This summary will use the number of subjects n, mean, standard deviation, minimum, median and maximum. Changes from baseline will be analyzed by the number of subjects n, mean and standard deviation and t-test or Wilcoxon rank sum test, as applicable.

The individual blood iCa²⁺ concentrations will further be displayed graphically over time for each of the two treatment groups.

A MMRM analysis will be deployed to evaluate differences between treatment groups in blood i Ca^{2+} concentrations that are collected at baseline, 1 hour and every 6 hours during the 120 hours Evaluation period and at 120 hours or end of the Evaluation period from the initiation of CRRT. The model will include the illness severity score APACHE II, baseline i Ca^{2+} concentration, treatment group and time point as fixed effects, and an interaction between time point and treatment group will be included in the model only if treatment effects differ statistically significantly over time (p < 0.01).

In addition, frequencies and percentages will be provided for $iCa^{2+} < 1.1 \text{ mmol/L}$ by time point and treatment group (threshold indicative of decrease in iCa^{2+} despite adequate calcium compensation).

Daily delivered dose and overall delivered dose (both in mL/kg/hour) will be summarized using the number of subjects n, mean, standard deviation, minimum, median and maximum, as applicable. Treatment exposure will be analyzed carrying out the same descriptive summary for the percentages of the prescribed dose actually administered to the patient.

Effluent rate is considered an appropriate surrogate for the CRRT dose. Therefore, prescribed and delivered CRRT dose will be derived as follows based on the University of Alabama at Birmingham Continuous Venovenous Hemodiafiltration Protocol¹² used in the study:

$$Q_E = Q_{PBP} + Q_D + Q_{FR} + Q_R$$

where Q_E is the effluent rate (mL/hour),

Q_{PBP} is the pre-blood pump infusion rate which is the Prismocitrate 18 flow rate (mL/hour),

Q_D is the dialysate flow rate (mL/hour),

Q_{FR} is the patient fluid removal rate (mL/hour), and

Q_R is the post-filter replacement fluid rate (mL/hour).

If one of the rate is missing, effluent rate will not be able to calculate.

The prescribed dose (effluent rate) is calculated as:

Prescribed Effluent Rate = Body Weight \times 25 mL/kg/hr

If there are multiple records of effluent rate per day (e.g. due to infusion rate change) the average value will be used to calculate the delivered dose for that day.

The percentage of the prescribed dose actually administered to the patient will be calculated by dividing the actual effluent rate by the prescribed effluent rate. Differences between treatment groups in the percentage of overall prescribed dose actually administered will be assessed on a 5% significance level using a two-sided t-test or Wilcoxon rank sum test, as applicable. However, the statistical test will only be carried out conditional upon a significant test result for the primary endpoint at the time point of the interim analysis or final analysis. This hierarchical test procedure guarantees that the overall Type I error is controlled and preserved at a maximum of 5%.

The analysis of secondary efficacy endpoints will be carried out on the FA based on the randomized treatment groups (intent-to-treat principle).

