14.3 Serum Bicarbonate, pH, Blood Total Calcium and Serum Electrolytes

Serum bicarbonate, pH (ABG), blood total calcium concentrations and serum electrolytes (sodium, potassium, chloride, phosphate, magnesium) will be analyzed in the exact same manner as blood iCa²⁺ concentrations.

Along the lines of Section 13.3 Secondary Analysis descriptive summaries will be carried out for each parameter at the different assessment time points, and changes from baseline will be analyzed. A MMRM analysis will be deployed for the different parameters following the description under Section 13.3.

The total calcium/iCa²⁺ ratio will only be summarized descriptively. Frequencies and percentages will be provided for pH < 7.2 by time point and treatment group (threshold indicative of metabolic acidosis). Frequencies and percentages will further be provided for total calcium/iCa ratio > 2.1 by time point and treatment group (threshold suggestive of citrate accumulation) as well as for anion gap > 11 mmol/L (threshold indicative of metabolic disturbance) and base excess < -5 mmol/L.

Complete blood count and blood lactate measurements obtained at screening will be listed by patient.

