Number of Adverse Events (Serious and Non-Serious)	
Number of Subjects With At Least One Adverse Event (Serious and Non-Serious) by MedDRA System Organ Class and MedDRA Preferred Term	
Number of Adverse Events (Serious and Non-Serious) by MedDRA System Organ Class and MedDRA Preferred Term	
Number of Subjects With At Least One Adverse Event (Serious and Non-Serious) by MedDRA System Organ Class, MedDRA Preferred Term and Severity	
Number of Subjects With At Least One Study Product-Related Adverse Event (Serious and Non-Serious) by MedDRA System Organ Class and MedDRA Preferred Term	
Number of Study Product-Related Adverse Events (Serious and Non-Serious) by MedDRA System Organ Class and MedDRA Preferred Term	
Number of Subjects With At Least One Study Product-Related Adverse Event (Serious and Non-Serious) by MedDRA System Organ Class, MedDRA Preferred Term and Severity	
Serum Bicarbonate, pH, Base Excess and Corresponding Changes from Baseline	
Model Parameters of Mixed-Effects Model Repeated Measures Analysis of Base Excess.	
Model Parameters of Mixed-Effects Model Repeated Measures Analysis of Serum Bicarbonate	
Model Parameters of Mixed-Effects Model Repeated Measures Analysis of pH	
Blood Total Calcium Concentrations and Total/Ionized Calcium Ratio and Corresponding Changes from Baseline	
Model Parameters of Mixed-Effects Model Repeated Measures Analysis of Blood Total Calcium Concentration	
Serum Electrolytes and Corresponding Changes from Baseline	
Model Parameters of Mixed-Effects Model Repeated Measures Analysis of Anion Gap	
Model Parameters of Mixed-Effects Model Repeated Measures Analysis of Sodium	

Table Number	Table Name
Table 14.3.5.8	Model Parameters of Mixed-Effects Model Repeated Measures Analysis of Potassium
Table 14.3.5.9	Model Parameters of Mixed-Effects Model Repeated Measures Analysis of Chloride
Table 14.3.5.10	Model Parameters of Mixed-Effects Model Repeated Measures Analysis of Phosphate
Table 14.3.5.11	Model Parameters of Mixed-Effects Model Repeated Measures Analysis of Magnesium
Table 14.3.5.12	Vital Signs and Corresponding Changes from Screening
Table 14.3.5.13	Model Parameters of Analysis of Covariance (ANCOVA) Model of Systolic Blood Pressure
Table 14.3.5.14	Model Parameters of Analysis of Covariance (ANCOVA) Model of Diastolic Blood Pressure
Table 14.3.5.15	Model Parameters of Analysis of Covariance (ANCOVA) Model of Mean Arterial Pressure

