2. LIST OF TABLES, FIGURES AND LISTINGS

Table Number	Table Name
Table 14.1.1	Subject Overview
Table 14.1.2	Categorical Demographic Characteristics at Baseline
Table 14.1.3	Continuous Demographic Characteristics at Baseline
Table 14.1.5	Vital Signs at Screening/Baseline
Table 14.1.6	Laboratory Parameters at Baseline
Table 14.2.1	Delivery of Prescribed CRRT Dose Based on Daily Delivered Dose
Table 14.2.2	Treatment Exposure (Categorical)
Table 14.2.3	Treatment Exposure (Continuous)
Table 14.2.4	Kaplan-Meier Survival Estimates for the Primary Efficacy Endpoint (FA)
Table 14.2.5	Quartile Estimates for Kaplan-Meier Based Survival Estimates of the Primary Efficacy Endpoint (FA)
Table 14.2.6	Clustered Log-Rank Test over Treatment Groups for Kaplan-Meier Based Survival Estimates of the Primary Efficacy Endpoint (FA)
Table 14.2.7	Kaplan-Meier Survival Estimates for the Primary Efficacy Endpoint (PP)
Table 14.2.8	Quartile Estimates for Kaplan-Meier Based Survival Estimates of the Primary Efficacy Endpoint (PP)
Table 14.2.9	Clustered Log-Rank Test over Treatment Groups for Kaplan-Meier Based Survival Estimates of the Primary Efficacy Endpoint (PP)
Table 14.2.10	Patient and Extracorporeal Circuit Ionized Calcium Concentrations (iCa ²⁺) and Corresponding Changes from Baseline
Table 14.2.11	Model Parameters of Mixed-Effects Model Repeated Measures Analysis of Patient Ionized Calcium Concentrations (iCa ²⁺)
Table 14.2.12.1	Subject Frequency of iCa ²⁺ < 1.1 mmol/L by Time Point
Table 14.2.12.2	Subject Frequency of pH Measurements Below the Threshold Indicative of Metabolic Acidosis (pH < 7.2)
Table 14.2.12.3	Subject Frequency of Total Calcium/iCa ²⁺ Ratio Above the Threshold Suggestive of Citrate Accumulation (Total Calcium/iCa ²⁺ Ratio > 2.1)
Table 14.2.12.4	Subject Frequency of Anion Gap Above the Threshold Indicative of Metabolic Disturbance (Anion Gap > 11 mmol/L)
Table 14.2.12.5	Frequency of Base Excess < -5 mmol/L
Table 14.2.13	Percentage of Prescribed Dose Actually Administered to the Patient

Table Number	Table Name
Table 14.2.14	Sensitivity Analysis: Kaplan-Meier Survival Estimates for the Primary Efficacy Endpoint
Table 14.2.15	Sensitivity Analysis: Quartile Estimates for Kaplan-Meier Based Survival Estimates of the Primary Efficacy Endpoint
Table 14.2.16	Sensitivity Analysis: Clustered Log-Rank Test over Treatment Groups for Kaplan-Meier Based Survival Estimates of the Primary Efficacy Endpoint

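### SAP 13.3 (and 14.3) uses baseline as both a response time and a covariate in the MMRM, which pulls the common treatment difference toward zero and departs, undeclared, from protocol 8.5.2 and 8.6

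*SAP*

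**What the plan says.** SAP 13.3 describes the mixed model for blood ionized calcium (iCa) as comparing the arms in "concentrations that are collected at baseline, 1 hour and every 6 hours during the 120 hours Evaluation period" and at the end of the period. Its next sentence sets the fixed effects: "The model will include the illness severity score APACHE II, baseline" iCa, treatment group and time point. It adds that "an interaction between time point and treatment group will be included in the model only if treatment effects differ statistically significantly over time", with p < 0.01 as the threshold. No covariance structure is named.

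SAP 14.3 covers bicarbonate, pH, total calcium and five electrolytes: "A MMRM analysis will be deployed for the different parameters following the description under Section 13.3". The table lists add base excess and anion gap ("Model Parameters of Mixed-Effects Model Repeated Measures Analysis of Anion Gap"), which makes 11 modelled parameters with iCa. The planned output for iCa is titled "Model Parameters of Mixed-Effects Model Repeated Measures Analysis of Patient Ionized Calcium Concentrations".

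The protocol differs. Section 8.5.2 models change from initiation of study CRRT in systemic iCa at 1 hour and six-hourly thereafter. Section 8.6 models change from baseline in the labs at times after initiation. Neither counts baseline as a modelled time. SAP 12 states that nothing has changed from the protocol.

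**The concern.** Read as written, each patient's baseline value sits on the left of the model as one of the responses and on the right as a covariate. On that row the covariate explains the response perfectly, so no treatment effect can remain. A model with one common treatment effect then averages a built-in zero with the effects after start.

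Two things are at stake. The MMRM difference for systemic iCa, a secondary efficacy measure, and for the metabolic safety labs would be reported too small, with an interval placed too close to zero. For safety labs that is the unwelcome direction. Second, a constant effect after start looks like one that changes over time, because it is zero at baseline, so the interaction rule can be triggered by the baseline row alone. The treatment parameter then changes meaning, and the SAP does not say which contrast will be reported.

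**Working it through.** **Inputs from the documents.** 80 patients per arm (SAP 5.2); gate at p < 0.01 (SAP 13.3); no imputation (SAP 8.2). Scheduled post-start times m (SAP Table 2): 21 for iCa (1 h plus 20 six-hourly draws) and 20 for labs without the 1 h draw. **Assumptions.** A treatment effect d, constant after start, and the correlation and stopping patterns below. The documents give no figure for this model, so there is none to reproduce.

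**1. Mechanism.** With balanced data the common treatment coefficient is Σ wⱼβⱼ, where the wⱼ are generalized-least-squares weights that sum to 1. On the baseline row β₀ = 0, so a constant effect d is estimated as d(1 − w₀).

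**2. Compound symmetry, complete data.** w₀ = 1/(m+1): 1/22 = 4.5% for iCa and 1/21 = 4.8% for the six-hourly labs. The patient mean over all rows is (y₀ + m × post-start mean)/(m+1). Given y₀, its treatment coefficient and its residual SD are both multiplied by m/(m+1), which is 0.955 or 0.952. The SE therefore shrinks in step and z is identical.

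**3. AR(1), equal spacing, complete data.** w₀ = 1/[2 + (m−1)(1−ρ)].
- ρ = 0.7: 1/8 = 12.5% (m = 21); 1/7.7 = 13.0% (m = 20).
- ρ = 0.8: 1/6 = 16.7% (m = 21).

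Here the SE does not follow the estimate. REML simulation, m = 21, assumed d = 0.3 SD, with versus without the baseline row:

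| ρ | Estimate | SE | z |
|---|---|---|---|
| 0.7 | 0.269 vs 0.306 | 0.071 vs 0.074 | 3.77 vs 4.17 |
| 0.8 | 0.239 vs 0.286 | 0.082 vs 0.085 | 2.92 vs 3.39 |

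Further runs gave z 3.11 vs 3.57 at ρ = 0.8, and at ρ = 0.9 z 2.52 vs 3.13 with power 76.5% vs 92.5%.

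**4. Early stopping.** Fewer post-start rows give the baseline row more weight. Under compound symmetry the simulated shrinkage for iCa is 5.8% if patients exit evenly over 72–120 h and 12.8% if median exit is 48 h (labs 6.2% and 15.4%). With about 8 post-start rows per patient on average:
- compound symmetry: 0.2355 vs 0.2834, a loss of 16.9%; z 2.93 vs 2.98;
- AR(1), ρ = 0.8: 0.2086 vs 0.2931, a loss of 28.8%; z 2.15 vs 2.76.

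In clinical units, for an assumed iCa effect of −0.050 mmol/L with between/within SD 0.07/0.06 (compound symmetry):
- full follow-up: −0.0473 vs −0.0496, a loss of 0.0023;
- exit 72–120 h: −0.0466 vs −0.0495, a loss of 0.0029;
- median exit 48 h: −0.0433 vs −0.0497, a loss of 0.0064.

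**5. Interaction gate.** Under compound symmetry with complete data, the noncentrality is (n/2) × d² × [m/(m+1)]/(1 − ICC) on m numerator degrees of freedom. For n = 80, d = 0.5, m = 21 the numerator is 40 × 0.25 × 0.955 = 9.55. Dividing by 0.7, 0.5 and 0.3 gives 13.6, 19.1 and 31.8 for ICC 0.3, 0.5 and 0.7. The gate opens in 30%, 51% and 86% of trials (simulation: 32%, 53%, 84%). At d = 0.3 it opens in 6–23%. At d = 0, or with post-start rows only, it stays near 1% when the covariance is modelled correctly.

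**6. Unstructured matrix, no interaction.** Baseline slope 1 with zero treatment and APACHE II coefficients makes every baseline residual zero, so the likelihood has no maximum. In one simulated data set (d = 0.5, m = 21) the treatment estimate fell from 0.50 to 0.0015 by iteration 12 and was still falling. Without the baseline row it settled at 0.517.

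**The case against.** The best reply is that the baseline phrase merely echoes the sampling schedule in SAP 5.5.2. The protocol models post-initiation change, the SAP is meant to elaborate the protocol, and SAP 12 reports no change, so the text could be loose wording. That is possible, but the sentence defines the values being compared by the model, and a programmer following it would include the row. The same edit settles either case.

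It is also fair that the size rests on assumptions. The larger early-stopping figures need exits well before the 72 hours that protocol 4.2 expects patients to remain on CRRT. For iCa, the absolute loss in the compound-symmetry scenarios above is small beside the 0.9–1.3 mmol/L target range.

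Four stronger or simpler inferences go beyond what the documents support:
- **That p-values are safe and only the estimate is wrong.** This holds under compound symmetry. The SAP names no structure, and under AR(1) z and power fall.
- **That the gate's false-positive rate is inflated.** With no effect it stays near 1%. With baseline as a modelled time, an effect of zero there and d afterwards does differ over time, so the gate is detecting something real but uninformative.
- **That intervals from the SAP procedure under-cover to the extent seen in simulation.** At −0.050 the common-effect 95% CI covered 92.5% (full follow-up) and 82.3% (median exit 48 h). But the gate opened in 70.3% and 66.3% of those trials, so the common-effect model would often be replaced, and post-start contrasts are then not diluted. The coverage figures apply only where that model is retained.
- **That the trial's main conclusion is at risk.** It is not, as set out in the verdict.

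**Conclusion.** The specification is wrong as written and should be corrected. The double use of baseline is in SAP 13.3, reaches the safety labs through 14.3, departs from protocol 8.5.2 and 8.6, and is not declared in SAP 12. It biases a retained common treatment difference toward zero. The 1/(m+1) figure is exact for compound symmetry with complete data. The AR(1), early-stopping and gate figures depend on the assumed correlation, effect size, constancy of effect and follow-up.

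The reach is limited. The primary clustered log-rank test and its alpha are untouched. The formal hierarchy covers only delivered dose, where "the statistical test will only be carried out conditional upon a significant test result for the primary endpoint". The descriptive summaries and threshold frequencies are unaffected, and so are the simpler comparisons, for which "Changes from baseline will be analyzed by the number of subjects n, mean and standard deviation and t-test or Wilcoxon rank sum test" is planned.

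**What to change.** In SAP 13.3 and 14.3:
- model only post-initiation values as responses;
- use the pre-start value as covariate only: initiation for iCa and baseline for the labs, which matches the reference points of the protocol's change scores;
- report the average post-initiation treatment difference with its 95% CI, whether or not the interaction is retained.

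Record any remaining departure from protocol 8.5.2 and 8.6 in SAP 12. The p < 0.01 rule can stay, because without the baseline row it behaves close to nominal under a correctly modelled covariance.

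Two accompanying edits would help but are not part of the error: name the covariance structure with a fallback for non-convergence, and give a time-point rule for the additional blood draws that SAP 8.5 admits to the MMRM.

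The cost is SAP text and programming. No data are lost, because the baseline value stays in the model as a covariate. z is unchanged under compound symmetry with complete data, and was higher after the change in the AR(1) checks.
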